Sample Tracking, Management and Storage: After sample obtainment, processing and storage, samples will initially be batched sent to the University of Pittsburgh biological sample repository where it will be tracked, managed and stored until the necessary translational or mechanistic measurement are performed. The CCC and DCC have a long track record of coordinating such processes.

Power Analysis: The prospective cohort study will utilize time to 4 hour mortality for its primary outcome to power the study. Based upon the 6 LITES Network sites admission history that will be utilized and their respective volume of hemorrhagic shock patients meeting inclusion and exclusion criteria and a 3.5 year enrollment time period, we plan to initiate sampling on 1,050 patients over the enrollment time period of the study. With an 85% consent rate which is an estimate based upon prior studies of similar nature, we will consent for participation 892 patients for the study. With an estimate baseline rate of 4 hour mortality of 11.1 % derived from the PROPPR study, there will be 90% power to detect a hazard ratio of 1.9.

Calculations are based on the primary aim of the study based on the following assumptions:

- Type I error rate of 0.05
- Two-sided alternative hypothesis

Linking Investigations in Trauma and Emergency Services

Task Order 2: Shock, Whole blood and Assessment of TBI (SWAT)

- 6 sites will be involved, three whole blood and three component sites
- Each site will enroll 175 participants in 3.5 years of enrollment, of which, 85% will be eligible for the study (149)
- The calculations are based on Cox proportional hazard model
- A 4 hour event rate in the control (non-whole blood) group of 0.111

The power calculations for these secondary aims are presented below. When reporting the results of the analyses, caution will need to be taken with respect to the interpretation of the findings since they are secondary in nature.

The secondary outcomes in Aim 1B include binary outcome, continuous outcomes, and time to event outcomes. For the binary outcomes, the odds ratio that can be detected is presented in Table 1. For the continuous outcome, the effect size that can be detected is 0.13. Finally, for the time to event outcomes, the hazard ratio that can be detected over a range of event rates in the control group is also presented in Table 1.

Event Rate	.1	.2	.3	.4	.5	.6
Odds Ratio	1.76	1.56	1.49	1.46	1.46	1.48
Hazard Rate	2.69	1.70	.37	.30	.27	.30

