Hypothesis#1A: For the primary outcome, the time to death will be generated for each participant. Kaplan-Meier curves will be generated for each treatment group and a log-rank test will be used to compare the distribution of the cumulative proportion. A hierarchical Cox-proportional hazards regression model will be used to control for the within-institution clustering. The hierarchical Cox-proportional hazards regression model will then be used to assess the independent impact of whole blood on time to death after controlling for the clustering effect and potential confounding effects of baseline characteristics. The model will include main effects for whole blood usage and a propensity score for receiving whole blood. The propensity score for the use of whole blood will be generated using a boosted logistic regression model. The dependent variable in the model will be the use of whole blood and the independent variables will be the baseline characteristics of the population. The Cox-proportional hazards model will be used to estimate the cumulative probability of death 4 hours.

Hypothesis#1B: The analytic approach for the secondary outcomes included in Hypothesis#1B will vary based on the type of outcome. For binary outcomes (e.g., 12 hour and 24 hour mortality, death from exsanguination, incidence of MOF, nosocomial infection), the same analytic approach that was carried out for Hypothesis 1a will be implemented.

For continuous outcomes (e.g., transfusion ratios, blood transfusion requirements) a two-sided t-test for correlated means will be used to compare the means between those receiving and not receiving whole blood. A hierarchical analysis of variance model will be used to control for the within-institution clustering. The model will be used to assess the independent impact of whole blood after controlling for the clustering effect and the potential confounding. The model will include main effects for whole blood usage and propensity for receiving whole blood.

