Finally, for time to event analyses (e.g., time to hemostasis), a bivariate hierarchical Cox proportional hazards regression model will be generated to compare the time to event between those receiving and those not receiving whole blood. Again, the hierarchical model will be used to control for within-institution clustering. In a second step, to determine the independent effect of whole blood after controlling for potential confounding effects, the propensity score will be added to the model.

Hypothesis#1C: A two-sided z-test for correlated proportions will be used to compare the distribution of GOS-E proportions between those receiving and not receiving whole blood. This

Linking Investigations in Trauma and Emergency Services

Task Order 2: Shock, Whole blood and Assessment of TBI (SWAT)

test will be used to control for the within-institution clustering. A hierarchical polytomous logistics regression model will then be used to assess the independent impact of whole blood after controlling for the clustering effect and the potential confounding effects of baseline characteristics. The model will include main effects for whole blood usage and propensity for receiving whole blood.

AIM#2: The analyses for the second aim will be restricted to the subset of participants who will be characterized as having a traumatic brain injury.

Hypothesis#2A: The analysis will begin by comparing the baseline characteristics of those with a prehospital and acute phase resuscitation systolic blood pressure greater than or equal to 120 mmHg to those who do not. For discrete variables, proportions will be generated and a chi-squared test will be used to test for differences between the proportions. For continuous characteristics, means (medians) and standard deviations (interquartile ranges) will be calculated and t-test (Wilcoxon) test will be used to compare the means (distributions) among those who receive and do not receive whole blood.

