A two-sided z-test for correlated proportions will be used to compare the distribution proportions of GOS-E at 6-months between those with a prehospital and acute phase resuscitation systolic blood pressure greater than or equal to 120 mmHg to those who do not. A hierarchical polytomous logistics regression model will be used to control for the within-institution clustering. The model will be used to assess the independent impact of whole blood after controlling for the clustering effect and the potential confounding effects of baseline characteristics. As was done in Aim#1A, the propensity for a prehospital and acute phase resuscitation systolic blood pressure greater than or equal to 120 mmHg will be generated using a boosted logistic regression model which will include all baseline characteristics, including site and whole blood usage. The same analytic approach will be used to measure outcomes at discharge except a hierarchical logistic regression model will be used.

Hypothesis#2B: The area under the curve of systolic blood pressure during the prehospital and acute phase resuscitation will be generated for each study participant. The analysis will begin by comparing the baseline characteristics with the area under the curve. For discrete variables, bivariate linear regression models will be generated (area under the curve as the dependent variable and the discrete baseline characteristic as the independent variable). For continuous characteristics, the correlation will be assessed.

Hierarchical models will be used to adjust for within-institution clustering. Hierarchical bivariate linear regression models will be used to assess the association of baseline characteristics associated with area under the curve. A stratified propensity analysis will be used to estimate the association of area under the curve with GOS-E at six months. A hierarchical linear regression

Linking Investigations in Trauma and Emergency Services

Task Order 2: Shock, Whole blood and Assessment of TBI (SWAT)

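### Tests named for correlated (paired) means and proportions are prescribed for independent patient groups with no pairs defined, so the unadjusted secondary comparisons in 1B, 1C and 2A are undefined as written

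*Combined protocol and SAP*

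**What the plan says.** Three places in the Analyses section of the combined protocol and SAP name a test for correlated data.

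- Hypothesis#1B, continuous outcomes such as transfusion ratios and requirements: "a two-sided t-test for correlated means will be used to compare the means between those receiving and not receiving whole blood". The next sentence gives clustering to a separate model: "A hierarchical analysis of variance model will be used to control for the within-institution clustering".
- Hypothesis#1C, GOS-E by whole blood use in TBI patients: "A two-sided z-test for correlated proportions will be used to compare the distribution of GOS-E proportions between those receiving and not receiving whole blood". Here the clustering role is given to the test itself ("test will be used to control for the within-institution clustering"), and then: "A hierarchical polytomous logistics regression model will then be used to assess the independent impact of whole blood".
- Hypothesis#2A, GOS-E by systolic pressure group: "A two-sided z-test for correlated proportions will be used to compare the distribution proportions of GOS-E at 6-months". A hierarchical polytomous model again follows and is given the clustering role.

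No formula, variance estimator or reference is given for either test. No matching is defined: the propensity score enters the 1B and 1C models as a term alongside whole blood use. The Power Analysis assumes that "6 sites will be involved, three whole blood and three component sites", with 149 counted patients each. The Whole Blood Transfusion Sites section instead expects whole blood sites to supply 33% of the cohort.

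**The concern.** A paired t-test works on within-pair differences, and a test for correlated proportions works on discordant pairs. Both need each observation in one group to be linked to one in the other. Here the groups are different people and nothing links them. A programmer would have to invent pairs, discard patients, or substitute another test.

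The correlation that does exist is between patients of the same site. Where exposure largely follows site, that correlation lies within the groups and enlarges the standard error of the difference. Pairing across groups does nothing about it, so 1C's stated purpose would not be met by a standard paired test.

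For GOS-E there are two further mismatches. The scale has eight categories (Figure 5), and no cut-point is named that would turn it into a proportion. The Power Analysis also sizes the 1C and 2A comparisons on a nonparametric analysis of variance, which is a different test.

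**Working it through.** **1. The plan's detectable effect for continuous outcomes.** Inputs from the Power Analysis: effect size 0.13, total 1,190 for Aim 1, two-sided 0.05, 90% power. z-sum = 1.960 + 1.2816 = 3.2415.

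- Paired formula, 595 pairs: 3.2415/√595 = 0.133, which agrees with 0.13.
- Two independent groups of 595: 3.2415 × √(2/595) = 0.188. With 1:2 allocation it is 0.199.
- Power at a standardized difference of 0.13 with independent groups of 595: 0.13/√(2/595) = 2.242; 2.242 − 1.960 = 0.282; power 0.61.
- With the 892 consented patients given elsewhere in the same section, the detectable difference is 3.2415 × √(4/892) = 0.217, and power at 0.13 is 0.49.

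The odds-ratio row of the secondary power table reproduces with independent groups of 595 + 595 (power 0.898 to 0.903). The total of 1,190 split in two is therefore the basis of at least that row.

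**2. Cost of leaving out site clustering.** The documents give no ICC, so 0.01 to 0.05 is assumed. Whole blood use is taken to be set by site. Standard error ratio = √(1 + (m − 1) × ICC).

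| Comparison | m per site | ICC 0.01 | ICC 0.05 |
|---|---|---|---|
| 1B | 149 | √2.48 = 1.57 | √8.40 = 2.90 |
| 1C | 0.35 × 149 ≈ 52 | √1.51 = 1.23 | √3.55 = 1.88 |

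The 35% TBI share is from the Power Analysis. The 52 is before any loss at six months. No row is given for 2A, because patients above and below 120 mmHg can come from the same site.

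**3. Does pairing help or harm?** Type I error at nominal 0.05 was simulated for three against three sites of 149 (4,000 replicates):

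| ICC | Independent t-test | Arbitrary pairs across groups | Test on site means |
|---|---|---|---|
| 0 | 0.050 | 0.051 | 0.054 |
| 0.01 | 0.22 | 0.22 | 0.055 |
| 0.02 | 0.33 | 0.33 | 0.050 |
| 0.05 | 0.51 | 0.51 | 0.049 |

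Arbitrary pairing behaves like the ordinary independent test. The inflation comes entirely from ignoring site, and pairing neither corrects it nor adds to it.

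**The case against.** The best defence is that correlated here means correlated within a site. Section 1C says its test is there to handle clustering. Cluster-adjusted t- and z-tests exist, accept unequal groups and can give valid standard errors. That stands as a possible intention for 1C. It has no textual support in 1B or 2A, where the clustering role goes to the model that follows. Even in 1C the method is not identified. A reader might infer that the tests cannot be computed under any reading; the documents support only that they are undefined as written.

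A reader might also take the 0.13 as proof that a paired formula was used. It is not. The effect-size metric is not named, and 0.133 also arises as a standardized difference with 1,190 per group, or as Cohen's f on an effective total of 595 (for example, 1,190 with a design effect of 2). The figure needs explaining, but it does not settle what was meant.

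A third tempting inference is that a paired formula would shrink the standard error. The simulation does not bear this out: unrelated pairs have an expected covariance of zero.

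It is also fair to say that the groups in 1B and 1C are defined by receipt of whole blood, so one site may contribute to both. The multipliers would then be smaller. Three against three equal sites would give equal group sizes, contrary to the 33% share, but equal counts would still not create pairs.

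Finally, the hierarchical models carry the adjusted conclusions, the polytomous model accommodates all eight GOS-E levels, and the Power Analysis already asks for caution on secondary findings. All of this stands and limits the reach of the point.

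**Conclusion.** The tests named in 1B, 1C and 2A do not match the data they are to be applied to, and a standard paired test would not do what 1C says. On an assumed ICC of 0.01 to 0.05, with whole blood use largely set by site, an unclustered comparison understates the standard error by a factor of about 1.6 to 2.9 in 1B and about 1.2 to 1.9 in 1C. No multiplier is claimed for 2A.

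The damage is confined to unadjusted secondary comparisons. A reader might infer that the primary result is compromised. It is not affected by this point, because 4-hour mortality is analysed by log-rank and a hierarchical Cox model, and the binary 1B outcomes are assigned that same approach.

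Separately, 0.13 is not a standardized difference detectable at 90% power with two independent groups totalling 1,190. That figure is 0.188, before any allowance for clustering. The change should be made, but it is a correction to secondary analyses and not a threat to the design.

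**What to change.** Delete the three correlated-data tests. Take the unadjusted comparison from the hierarchical model that the plan already names: linear or analysis of variance for 1B, polytomous logistic for 1C and 2A. Fit it first without and then with the propensity score. The plan already does this for time to hemostasis under Hypothesis#1B, so no new method is needed. In 2A, name the blood-pressure group as the exposure term, since the current model sentence refers to whole blood.

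Bring the GOS-E test in the Power Analysis into line with the analysis. Restate 0.13 with its metric, group sizes and clustering assumption, and reconcile 1,190 with 892.

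A cumulative logit for GOS-E, or a small-sample reference for six sites, are separate decisions and are not required here.

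The cost is SAP wording, one recalculated power statement, and unadjusted intervals that are wider than an unclustered test would give.

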Component Transfusion Sites: Busy, Level 1 trauma centers from within the LITES Network will be selected based upon the ability to enroll patients with the proposed inclusion and exclusion criteria who currently utilize initial ratio based resuscitation (1:1:1 or 1:1:2) for patients at risk of large volume transfusion and are able to perform all necessary requirements for the planned prospective cohort study proposed. There is the potential for sites to differ based upon their current massive transfusion protocol and these standard practices will be documented for each site.

Primary TBI Subgroup Stratification: Presence or absence of Traumatic Brain Injury (TBI) will be the principle subgroup stratification for the study. Presence of TBI will be based upon CT imaging results (classification: subarachnoid, subdural, intracerebral hemorrhage, intracranial injury, epidural, +/- shift, multifocal with specific classification) and TBI severity will be characterized and grouped by GCS, Abbreviated Injury Severity (AIS) coding, ICD-10 head region severity scores

Linking Investigations in Trauma and Emergency Services

Task Order 2: Shock, Whole blood and Assessment of TBI (SWAT)

and Rotterdam CT scores. The data coordinating center will collect de-identified serial head CT images (first two performed) from all participating sites in patients with a head abbreviated injury score of 2 or greater (head AIS >2). These images will allow the determination of Rotterdam CT head scores to appropriately classify traumatic brain injury severity. Serial head CTs (first two) will also be assessed for progression of injury. An independent and blinded neuroradiologist from the University of Pittsburgh will provide the classification of brain injury.

Due to the nature of the population being studied, there will be patients who have clinically evident TBI but who do not have a head CT completed due to clinical intervention being a higher priority than diagnostic imaging. Often when patients require urgent clinical interventions, diagnostic scans (including CTs) are deferred until the patient is stabilized and the emergent issue is resolved. Unfortunately, this means that sometimes a patient expires during intervention, and a CT is never obtained. Therefore, patients who present in extremis with a clinically obvious TBI (eg: unhelmeted motorcyclist, falls from height, etc.) will be included in the TBI sub-group even if they do not have head CTs completed.

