- For Aim 1C, a nonparametric analysis of variance will be used to compare the distribution of the GOS-E between the two groups. An effect size of 0.17 could be detected.
- For aim 2A, a nonparametric analysis of variance will be used to compare the distribution of the GOS-E between the two groups. An effect size of 0.28 could be detected.
- For aim 2B, a nonparametric correlation coefficient will be used to assess the association between GOS-E and the area under the systolic blood pressure curve. For each, a 95% confidence interval with a width of 0.19 can be estimated.
- For all secondary analyses, the type I error rate was set to 0.05, with a two-sided alternative hypothesis, and 90% power. For the Aim 1, the sample size will be 1,190. For Aim 2, the sample size will be limited to those with a traumatic brain injury. For the purposes of this study, this is expected to be 35% or a total of 417 participants.

Analyses

AIM#1: The analysis will begin by describing the baseline demographic and clinical characteristics of the overall population and then stratified by whole blood usage. The characteristics will be

Linking Investigations in Trauma and Emergency Services

Task Order 2: Shock, Whole blood and Assessment of TBI (SWAT)

compared among those who receive and who do not receive whole blood. For discrete variables, proportions will be generated and a chi-square test will be used to test for differences between the proportions. For continuous characteristics, means (medians) and standard deviations (interquartile ranges) will be calculated and t-tests (Wilcoxon) will be used to compare the means (distributions) among those who receive and do not receive whole blood.

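### The Hypothesis 1C GOS-E model adjusts for prognosis only through the whole-blood propensity score, with no direct term for presenting GCS or age

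*Combined protocol and SAP*

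**What the plan says.** Under Analyses, Hypothesis#1C, GOS-E is first compared between groups with a test for correlated proportions and then modelled with a hierarchical polytomous logistic regression. Of the model terms the plan says: "The model will include main effects for whole blood usage and propensity for receiving whole blood". The stated purpose is to allow for site clustering and for confounding by baseline characteristics.

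The primary Cox model under Hypothesis#1A has the same two-term form: "The model will include main effects for whole blood usage and a propensity score for receiving whole blood". That section also defines the score as a boosted logistic model of whole-blood use on the population's baseline characteristics. It does not list them.

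The data needed for direct adjustment are collected. Age is under Demographic and Injury Data, and GCS is under Prehospital Data and ED Data. The plan itself treats GCS as a severity measure. Under Primary TBI Subgroup Stratification it says that "TBI severity will be characterized and grouped by GCS, Abbreviated Injury Severity (AIS) coding", together with other head-injury scores.

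On power, the Power Analysis section states for Aim 1C: "An effect size of 0.17 could be detected". The general condition is: "For all secondary analyses, the type I error rate was set to 0.05, with a two-sided alternative hypothesis, and 90% power".

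**The concern.** A propensity score reduces the covariates to one number, weighted by how strongly each predicts treatment. Whole-blood sites and component sites are selected separately, three of each, so treatment is mostly decided by which hospital the patient reached. GCS and age may then carry little weight in the score however strongly they predict neurological outcome. Their contribution to GOS-E stays in the residual.

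Two losses can follow. The whole-blood effect is estimated less precisely than the data allow. The test can also be conservative: the fitted score removes some chance imbalance in GCS and age, so the estimate varies less than its model-based standard error says.

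Both losses fall on an outcome measured only in the TBI subset, where patients are fewest.

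**Working it through.** **Inputs from the documents.** Two-sided type I error 0.05 and 90% power for secondary analyses. Aim 1C effect size 0.17, scale not stated. Sample size: "For the Aim 1, the sample size will be 1,190". TBI subset: "this is expected to be 35% or a total of 417 participants". The primary power statement gives a smaller total: "we will consent for participation 892 patients for the study", and 0.35 × 892 = 312. Allocation is three sites against three (about 1:1 if sites enrol equally), or 33% whole blood according to the site-selection text.

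**Inputs assumed.** Share of outcome variance explained by GCS and age (R²), the odds ratio and the intraclass correlation (ICC). None is in the documents.

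**Step 1: the plan's own figure.** Detectable d = (1.960 + 1.282) × √(k/N), with k = 4 for 1:1 and k = 4.5 for 33% whole blood.
- N = 1,190, 1:1: 3.242 × √(4/1,190) = 0.188.
- N = 1,190, 33% whole blood: 3.242 × √(4.5/1,190) = 0.199.
- The stated 0.17 is not reproduced. It comes close at 80% power with a rank test (efficiency 0.955): 2.802 × √(4/1,190) / √0.955 = 0.166.
- Read as d = 0.17 in the 417 TBI patients at 1:1: 0.17 / √(4/417) = 1.736, so power is Φ(1.736 − 1.960) = 41%. With 312 it is 32%.

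The stated 90% is therefore not a sound base for a gain in Hypothesis 1C. Taken at face value, it allows +5.2 points at R² = 0.2, since Φ(3.242/√0.8 − 1.960) = 95.2%. At R² = 0.4 it allows +8.7 points.

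**Step 2: score alone against score plus GCS and age, no site variance.** Simulation with 312 TBI patients, 156 per group, an eight-level outcome, rank regression in place of the ordinal model, a boosted score on six covariates, and 3,000 data sets per row.

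| R² (ranks) | Conditional OR | Score only | Score + GCS + age | Gain (points) |
|---|---|---|---|---|
| 23% | 1.8 | 66.3% | 75.0% | 8.7 |
| 23% | 2.0 | 82.2% | 88.2% | 6.0 |
| 35% | 1.8 | 54.1% | 71.6% | 17.5 |
| 35% | 2.0 | 69.3% | 83.8% | 14.5 |
| 23% | 1.0 (null) | 3.2% | 4.4% | – |
| 35% | 1.0 (null) | 2.2% | 4.6% | – |

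A separate simulation at 33% whole blood and OR 1.8, with R² about 0.22 and 0.35, gave 65% to 74% and 55% to 70% with 312 patients. With 417 it gave 78% to 85% and 66% to 82%. Across such runs the gain is roughly 5 to 20 points.

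**Step 3: when the score already carries the prognosis.** Proportional-odds simulation, N = 417, log odds ratio 0.48, 500 runs per setting, comparing the score with GCS and age entered directly.
- GCS and age unrelated to receipt: 66.6% to 72.4% (R² 0.2) and 55.8% to 65.8% (R² 0.4).
- The same combination of GCS and age driving both receipt and outcome: 71.6% to 72.2% and 69.2% to 69.6%. Here the score is the outcome predictor by construction, so there is almost nothing to recover.

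**Step 4: between-site variance.** With three sites per group and m patients per site, Var(difference) = (2/3) × [ICC + (1 − ICC)(1 − R²)/m]. As an illustration take d = 0.28, the size stated for Aim 2A. The baseline here has no covariate adjustment, and the normal approximation is used.

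| ICC | N = 417, R² 0.2 to 0.4 | N = 312, R² 0.2 to 0.4 |
|---|---|---|
| 0 | +7.6 to +14.3 | +9.4 to +19.5 |
| 0.01 | +5.4 to +11.6 | +5.8 to +12.8 |
| 0.03 | +2.1 to +4.4 | +2.3 to +5.1 |
| 0.05 | +1.0 to +2.1 | +1.2 to +2.5 |

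Worked cell, N = 417 (m = 69.5), ICC 0.05. Without covariates the variance is (2/3)(0.05 + 0.95/69.5) = 0.0424, z = 0.28/0.206 = 1.36, power 27.4%. At R² = 0.2 power is 28.4%.

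Simulations with a site standard deviation of 0.3 log-odds (latent ICC = 0.09/(0.09 + 3.29) = 0.027) and a site-level test agree: gains of about 1 to 4 points in one and 5 to 6 in another.

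**The case against.** The strongest objection is that a propensity score built from baseline characteristics is a recognised way to control confounding in a cohort. It would ordinarily include age and presenting GCS, so the plan does not ignore them. This stands. A reader might infer that the two variables are left out altogether, and the text does not support that. What is missing is a direct term, and the consequence shown is for precision and for the calibration of the test. Bias has not been shown.

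A reader might also infer a fixed loss of 9 to 17 points. That holds only for the odds ratio of 1.8 with no site effect. At 2.0 the same simulation gives 6.0 and 14.5. From the plan's stated 90% no gain can exceed 10 points. The 90% does not reproduce, so it is a weak ceiling, but this does not turn a conditional range into a fixed number.

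The site objection is the most damaging to the size. Treatment follows site, and GCS and age do not remove between-site variance unless sites differ in case mix. Zero site variance is the most favourable assumption, and Step 4 shows the gain shrinking quickly as it is relaxed.

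The Hypothesis#2A section describes a propensity model that includes site and presents it as following Aim 1A. If site also enters the whole-blood score, the score nearly reproduces treatment. In a simulation of that case the whole-blood test rejected 0% of the time with or without GCS and age. The plan does not say whether site is in the whole-blood score.

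Finally, the plan says only polytomous, and Hypothesis#2B uses the word multinomial. An unordered eight-level model needs seven coefficients per covariate, so 14 for two covariates. The fix is cheap only in an ordered model.

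**Conclusion.** The point holds in a limited form. The Hypothesis 1C model adjusts for baseline prognosis only through the propensity to receive whole blood. That score need not capture presenting GCS and age as predictors of GOS-E, although both are recorded.

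With R² of about 20–40%, a conditional odds ratio of 1.8–2.0, no between-site variance, and receipt not already driven by the prognostic combination of GCS and age, direct adjustment is worth roughly 5 to 20 points of power. The null rejection rate moves from about 1–3% to about 4–5%. With an ICC of about 0.03–0.05 the gain is about 1 to 6 points. All of these inputs are assumptions.

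The primary Cox model has the same two-term form, and a reader might extend the claim to it. No calculation here supports that extension, so it remains a suggestion.

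**What to change.** In the Hypothesis 1C section, pre-specify first recorded GCS (prehospital or arrival) and age as covariates beside whole blood, the propensity score and the site term. State that the model is an ordered, cumulative-logit one, so that each covariate adds a single slope. List the variables in the whole-blood propensity score and say whether site is among them. Restate the Aim 1C power on the TBI sample, reconciling 1,190 with 892 and so 417 with 312, and show the R² and ICC assumed.

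The cost is SAP wording, two more coefficients and a proportional-odds assumption that should be checked. No new data are needed. The same covariates could be considered for the primary Cox model, after a calculation of their effect there.
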